5.4. Procedures of monitoring subject compliance

Administration will be performed under medical supervision. A mouth control will be performed immediately after the administration.

6. ASSESSMENT OF PHARMACOKINETIC EVALUATION

6.1. Specification of the pharmacokinetic parameters

6.1.1. Plasma

The following pharmacokinetic parameters will be determined from DNDI-6148 concentrations:

- Main DNDI-6148 PK parameters:
 - o AUC_{0-∞} (h*ng/mL): area under the plasma concentration-time curve from administration up to infinity with extrapolation of the terminal phase;
 - o C_{max} (ng/mL): observed maximum plasma concentration,
- Other DNDI-6148 PK parameters:
 - o AUC₀₋₂₄: AUC from administration up to 24h
 - AUC_{0-t:} area under the plasma concentration-time curve from administration up to the last quantifiable concentration at time t
 - AUC_{0-t}/D: AUC_{0-t} divided by dose
 - o AUC_{0-∞}/D, : AUC_{0-∞} divided by dose
 - o C_{max}/D,: C_{max} divided by dose
 - o tmax_(h): first time to reach Cmax
 - o t_{1/2} (h): plasma elimination half-life
 - o MRT (h): Mean time of drug presence in plasma
 - o CL/F (mL/h): Apparent total clearance of the drug from plasma after oral administration
 - o Vz/F (L): Apparent volume of distribution
 - o ke: terminal elimination rate constant
 - o %AUCextra: % of AUC extrapolated

6.1.2. Urine

The amount and concentration of DNDI-6148 will be measured. The appropriate specific PK parameters to be calculated will be decided according to concentration.

The following parameters will be calculated from urine data for DNDI-6148:

- **Ae(0-t)** Total amount excreted over 24 h and 72 h (*i.e.* t = 24 or 72).
- **Fe** The fraction of the dose excreted in urine over 24 h and 72 h.
- CLr The renal clearance of DNDI-6148.

6.2. Methods and timing for assessing, recording, and analysing pharmacokinetic parameters

6.2.1. Collection, treatment and storage of blood samples

Blood sampling will be performed for DNDI-6148 concentration measurements at the exact time-points with an authorised time-window described in the Table 8:

Table 8 PK Sampling time

Day	Sampling time	Sample N°	Time window (min)
1	T0 (predose)	P00	+/-1
	T0h30min	P01	+/-1
	T1h00	P02	+/-1
	T1h30min ¹	P03 ¹	+/-3
	T2h	P04 ¹ or P03 ²	+/-3
	T2h30min	P05 ¹ or P04 ²	+/-5
	T3h	P06 ¹ or P05 ²	+/-5
	T4h	P07 ¹ or P06 ²	+/-5
	T5h	P08 ¹ or P07 ²	+/-5
	T6h	P09 ¹ or P08 ²	+/-5
	T9h	P10 ¹ or P09 ²	+/-5
	T12h	P10 ²	+/-5
2	T24h	P11	+/-15
3	T48h	P12	+/-15
4	T72h	P13	+/-15
5 ²	T96h	P14	+/-30
6 ²	T120h	P15	+/-30

¹ for the cohorts 10 mg, 20 mg, 40 mg and 80 mg $\,$

Blood handling procedures: at each time point indicated in the table, a 6 mL blood sample should be drawn into K_2EDTA tube. The blood samplings will be carried out on Day 1 by means of a catheter, and on the other days of the study using a single-use needle.

The blood samples will be gently inverted a few times for complete mixing with the anticoagulant. The exact time of sample collection will be recorded on the eCRF. Within 30 minutes following blood collection, centrifuge each blood sample at 1500 g for 10 minutes at $4^{\circ}C$.

² for the cohorts 160 mg, 260 mg, 380 mg and 500 mg

Immediately after the end of centrifugation, the top layer of human plasma will be transferred into 2 prelabelled polypropylene tubes prefilled with phosphoric acid (H_3PO_4) 2% (1/1 v/v). The two tubes will contain 500 μ L of plasma each for PK analysis (primary and backup tubes).

Tubes will be capped immediately for each time point and the plasma will be frozen in an upright position at -80°C (+/- 10°C) for storage. In case of temperature deviation, the total time spent above -20°C should not exceed 4 hours.

The remaining plasma (approx. 2 mL) shall be used for metabolite identification: it will be transferred in 2 pre-labelled polypropylene tube with H_3PO_4 2% (1/1 v/v) (twice 500 µL), and 1 pre-labelled polypropylene tube without H_3PO_4 (remaining volume, approx. 1 mL).

Tubes will be capped immediately for each time point and the plasma will be frozen in an upright position at -80°C (+/- 10°C) for storage.

Blood cells should not be transferred. All sample tubes must be clearly and appropriately labelled.

6.2.2. Collection, treatment and storage of urine samples

Urine collection will be performed for DNDI-6148 urine concentration measurements, at the following time points: predose,]D1T0h – D1T12h],]D1T12h – D2T24h],]D2T24h – D3T48h] and]D3T48h – D4T72h].

Urine handling procedures:

Subjects will have to urinate in a polypropylene container. Weight will be measured and recorded for each urination. Within 5 minutes, urine will be transferred in a polypropylene container containing 20 g of citric acid monohydrate. This container will be mixed vigorously to dissolve citric acid. This container will be kept at 4°C for a maximum of 43 hours. During the interval period, each urination will be added in this container. At the end of the interval period, the pool of acidified urine will be vigorously mixed and two aliquots will be prepared each with 1 mL of acidified urine and 1mL of aqueous solution of BSA 50 g/L and NaCl 9 g/L.

The tubes containing the mixture acidified urine/BSA will be capped immediately for each time point and the mixture acidified urine/BSA will be frozen in an upright position at -80°C (+/- 10°C) for storage. In case of temperature deviation, the total time spent above -20°C should not exceed 4 hours.

6.2.3. Transport of samples

Samples will be sent to laboratory SGS Wavre, Belgium, attention to [name], for analysis. The shipment will be done in dry ice by a specialized carrier. Temperatures will be monitored using data logger during all transport. The primary samples will be sent separately from the back-up samples. The back-up samples will be shipped with the subsequent cohort samples.

6.3. Analytical methods

A validated internally standardized liquid chromatography tandem mass spectrometry (LC/MS-MS) method will be used for the analysis of DNDI-6148 in acidified K₂EDTA human plasma and acidified human urine.

The Lower limit of quantification (LLOQ) of DNDI-6148 in plasma is 1 ng/ml in plasma and 10 ng/ml in urine.

Bioanalysis will be carried out at SGS Life Sciences, Wavre, Belgium. The bioanalytical procedures of the laboratory are certified according to Good Laboratory Practice (GLP).

7. ASSESSMENT OF PHARMACODYNAMIC EVALUATION

Subjects will be resting in a quiet supervised setting with minimal stimulation (e.g. no television, loud music, computer games, cell phones, handled music player, etc.) and lay in a supine position for 15 min $_{\text{Temp-UPC-853-C}}$ du 07/08/2017

before each nominal PK time point for the duration of the ECG sampling period. The ECG extraction window will precede any PK blood draw (within 10 minutes prior to PK sampling). All other exams should be done after the ECG extraction period.

Holter recordings will be archived. Analyses will be conducted at the end of the trial by Banook Groupe, Nancy, France if decision to progress to Multiple Ascending Dose (MAD) study is taken or after MAD in order to pool data from SAD and MAD studies. Subjects will be in resting position from -70 to -15 minutes prior to dosing in order to insure proper quality of the recording for ECG extraction pre-dose at T-60 min, T-40min and T-20min. Windows of ECG extractions for each timepoint are defined in the Banook Groupe Scope of Work document.

The Holter data collected in this trial will not be part of the trial's clinical data base.

In case the Holter extracted data are analysed, the following analyses are planned and will be reported in a separate report:

For each selected post-dose PK time-point, Triplicate ECG with at least a 1 min interval will be extracted from the Holter recording at the cardiac core laboratory at the following time points:

On D1 and on D1 to D2: T0 (pre-dose 3 times triplicate ECG as described above), T0h30min, T1h, T1h30 (only for the cohorts 10 mg, 20 mg, 40 mg, 80 mg), T2h, T2h30, T3h, T4h, T5h (only for the cohorts 160 mg, 260 mg, 380 mg and 500 mg), T6h, T9h, T12h, T24h. T0h corresponds to the administration time reference at which subjects will receive the study drug throughout the study (around 8:00 am).

The Holter-extracted triplicate parameters (RR, HR, PR, QRS, and QT) would be averaged to obtain one single value per time point. On Day 1, three pre-dose triplicates will be extracted and averaged to establish the baseline value.

Changes from baseline with the recorded Holter (Day 1) will be calculated for each parameter:

- Categorical analysis for QT, QTcF, QTcB, ΔQTcF and ΔQTcB according to the thresholds defined below.
- ECG morphological analysis.

The pre-defined thresholds for the categorical analysis for maximum actual values will be:

- QTc interval > 450 ms
- QTc interval > 480 ms
- QT/QTc interval > 500 ms

and for maximum changes from baseline:

- ΔQTc interval > 30 ms
- ΔQTc interval > 60 ms

All parameters and their changes from baseline will be summarized by dose regimen and time-point (including Δ HR, Δ RR, Δ PR, Δ QRS, Δ QT). Placebo group extracts will be used for the double-delta analysis of QT.

QT interval calculation would be manually checked by a cardiologist.

A concentration-response analysis between $\Delta QTcF$ and DNDI-6148 concentrations will be performed on ECG data issued from Holter extraction. $\Delta\Delta QTcF$ with their 90% CI will be estimated from the model at each dose Cmax geometric means.

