Physical examination, neurological examination, ECGs, vital signs and questionnaires: Physical examination, neurological examinations, ECGs, vital signs and questionnaires (C-SSRS, Bond and Lader VAS) recorded during the study will be individually listed and quantitative parameters will be summarised by using descriptive statistics. For vital signs and ECG parameters, all values recorded during the study will be individually listed and flagged for abnormalities and for clinical significance (assessed by investigator). In addition, values and abnormalities (not clinically significant and clinically significant) will be described by dose group and overall, at screening, study baseline (D-1, or D1 predose), each evaluation under treatment phase and at the end of the study. Change between the value at baseline and the value at each evaluation under treatment phase and at end of study visit will be described for each parameter by dose group and overall.

Laboratory parameters: All laboratory values recorded during the study will be individually listed and flagged for values outside reference ranges and for clinical significance (assessed by investigator). Quantitative parameters will be summarized by descriptive statistics. Values, position according to laboratory range and clinical significance assessment will be described at screening, D-1 (baseline) and at D2, D4 and D6 (only for the cohorts 160 mg, 260 mg, 380 mg and 500 mg) by dose group and overall. Change between the value at baseline and the value at post-dose visits will be described for each parameter by dose group and overall. All quantitative and qualitative urinary test results will be listed, sorted dose group, visit and subject.

Pharmacokinetic parameters:

Plasma concentrations will be summarized by dose level and time point. The derived PK parameters will be listed by subject and summarized by dose level.

In addition, the hypothesis that AUC and C_{max} are dose proportional will be formally tested using a power model approach.

Pharmacodynamic parameters:

ECG parameters will be summarized by dose level and time points on actual values and changes from baseline.

Placebo corrected changes from baseline ($\Delta\Delta$) will be calculated with their 90% CI for each dose level and time points and displayed.

Subjects meeting predefined criteria for ECG parameters abnormality and results of the morphological analysis will be summarized by dose level using count and percentage.

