2.3. Exploratory objective

- To determine PD effect on cardiologic parameters after single oral dose administered as oral suspension of DNDI-6148 in healthy male subjects.
- To identify DNDI-6148 main metabolites.

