3.1.3. Exploratory endpoints

> Pharmacodynamic evaluation

The following cardiological pharmacodynamics parameters of DNDI-6148 will be analyzed:

- RR, HR, PR, QRS, QT, QTcF, QTcB, ΔHR, ΔRR, ΔPR, ΔQRS, ΔQT, ΔQTcF and ΔQTcB.
- Identification of metabolites
- Exploratory identification of DNDI-6148 metabolites.

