8.1.1.3. Electrocardiogram (ECG)

Single 12-lead ECGs will be recorded after at least 10 minutes in supine position using a Cartouch Cardionics® Device (in case of abnormality, a retest is allowed at a minimum of one-minute interval between 2 subsequent ECG). Baseline assessment will be conducted in triplicate, at a minimum 1-minute interval between 2 subsequent ECG.

ECGs should always be recorded before the PK sampling (if any), except pre-dose and holter recording.

Each ECG consists of a minimum 10 second recording of the 12 leads simultaneously, leading to a 12-lead ECG (25 mm/s, 10mm/mV) print-out with morphology, HR, PR, QRS, QT, QTc automatic correction evaluation QTcB, QTcF, including date, time, year of birth and number of the subject, signature of the research physician, and at least 3 complexes for each lead. The Investigator medical opinion and automatic values will be recorded in the eCRF. This print-out will be retained at the site level.

Electronic recordings will be transferred to the ECG central reading facility at the end of each day. Safety cohort reports will be prepared at the end of each cohort, to be provided to the Safety Review Committee for dose-escalation decision. Central reading values will be transferred into the clinical database at the end of the study and will prevail on the automatic values for the final ECG analysis.

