In case, $AUC_{0-\infty}$ could not be considered as reliable in a majority of subjects (e.g. too large percentage of extrapolation, poor quality of k_e determination), dose proportionality assessment will be performed on AUC_{0-t} values.

The estimate obtained for β is a measure of dose proportionality. The estimate of β together with its 90% CI (β_{l} , β_{u}) will be presented to quantify the degree of non-proportionality.

The dose proportionality will be confirmed if the 90% CI of β (β_I , β_u) is contained completely within the following critical region:

$$\left[\Theta_{L};\Theta_{H}\right] = \left[1 + \frac{\log(0.8)}{\log(r)};1 + \frac{\log(1.25)}{\log(r)}\right]$$

where r, defined as the dose ratio, is equal to h/I, h being the highest dose and I the lowest dose.

In this decision rule, the dose proportionality will be analyzed as an equivalence problem. If the 90% CI is excluded completely from the critical region $\left[\Theta_L;\Theta_H\right]$ defined here above, the hypothesis of dose proportionality is rejected. If the 90% CI of β includes the lower or the upper bound of the critical region, no conclusion can be done on dose proportionality. The proportionality will be tested at a 5% significance level.

The calculation of the increase in AUC and C_{max} for a two-fold increase in dose will be performed by substituting the value of β in the equation 2^{β} . CI for this ratio will be obtained by substituting β_{l} and β_{u} in the equation 2^{β} .

Assessment of the dose proportionality will be performed on the complete dose range. In case of departures from linearity or of negative conclusion of dose proportionality on the complete dose range, further investigation using the same methodology might be done on a restrained dose range.

The statistical package SAS[®] v.9.4 will be used to perform all statistical analyses.

Pharmacodynamic

In case the Holter data are analysed, the following analyses will be reported in a separate report:

All ECG parameters for PD analysis will be extracted in triplicate from 24-hours Holter recording. Extraction will be matched to PK sampling time and triplicate values will be averaged in order to obtain one single value per time point. Individual data listings and descriptive statistics by dose level and time point will be performed.

All parameters will be presented descriptively and graphically on raw data and changes from baseline by dose level and time points.

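### The Synopsis promises placebo-corrected ECG changes with 90% CIs without condition, but Sections 7 and 11.1.3 run the cardiac PD analysis only if a multiple-dose study is decided on or has been done

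*Protocol*

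**What the plan says.** **Stated without condition.** Section 2.3 gives the objective: "To determine PD effect on cardiologic parameters after single oral dose administered as oral suspension of DNDI-6148 in healthy male subjects". Section 3.1.3 introduces the endpoints with "The following cardiological pharmacodynamics parameters of DNDI-6148 will be analyzed" and lists RR, HR, PR, QRS, QT, QTcF, QTcB and their changes from baseline. The Synopsis, under Pharmacodynamic parameters, has ECG values and changes summarised by dose and time. It says that placebo-corrected changes "will be calculated with their 90% CI for each dose level and time points and displayed", and adds counts of subjects meeting ECG abnormality criteria. Only the concentration-response analysis is called optional there.

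**Stated with a condition.** Section 7 archives the Holter recordings and has them analysed at the end of the trial "if decision to progress to Multiple Ascending Dose (MAD) study is taken or after MAD in order to pool data". It continues: "The Holter data collected in this trial will not be part of the trial's clinical data base", and "In case the Holter extracted data are analysed, the following analyses are planned and will be reported in a separate report". The PD part of 11.1.3 opens with "In case the Holter data are analysed, the following analyses will be reported in a separate report" and then says that all ECG parameters for the PD analysis come from Holter triplicates.

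**Collected in every case.** Section 8.1.1.3 provides for 12-lead ECGs with a triplicate baseline and central reading: "Central reading values will be transferred into the clinical database at the end of the study and will prevail on the automatic values". Section 11.1.2.2 describes ECG values, abnormalities and changes from baseline by dose group, as part of the safety analysis.

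**The concern.** The two sets of statements cannot both be carried out if there is no MAD study. A reader of the Synopsis expects a placebo-corrected cardiac result with intervals from this trial. A reader of Sections 7 and 11.1.3 finds that it may never be produced. If MAD does go ahead, the second branch in Section 7 allows the single-dose Holter data to wait until MAD is finished and then be pooled with it.

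At stake is whether the trial reports a formal comparison with placebo for its cardiac objective, or only within-group summaries. The protocol itself fixes both the condition and the data source, so this is not detail left to a statistical analysis plan.

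**Working it through.** The protocol gives no figure to reproduce, because Section 11.2 states that no formal sample size calculation was done. The check is a comparison of sections, then some counts.

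**1. Which analysis is conditional, and where**

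| Analysis | Synopsis | Section 7 | Section 11.1.3 | Produced without MAD? |
|---|---|---|---|---|
| Values and changes by dose and time | Unconditional | Holter, conditional | Holter, conditional | Only as 12-lead safety tables (11.1.2.2) |
| Placebo-corrected changes | Unconditional, 90% CI | Double-delta analysis of QT, conditional | Not listed by time point | No |
| Threshold counts | Unconditional | Conditional | Conditional | No |
| Concentration-QTcF model | Optional | Conditional | Conditional | No |

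Both timing options in Section 7 need a MAD study: one follows the decision to start it, the other its completion. No section provides for the PD analysis when neither applies.

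**2. Subjects affected**

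Table 7 has 8 cohorts of 6 active and 2 placebo. Active: 8 × 6 = 48. Placebo: 8 × 2 = 16. Total: 64, each with a 24-hour Holter.

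**3. What the 12-lead ECGs can supply**

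- Post-dose times in 8.2.2: 1, 2, 3, 4, 6, 9, 12, 24, 48 and 72 h = 10. The 160 to 500 mg cohorts add 96 and 120 h = 12.
- Holter extraction times in Section 7: 11 post-dose times in every cohort. At 10 to 80 mg these are 0.5, 1, 1.5, 2, 2.5, 3, 4, 6, 9, 12 and 24 h. At 160 to 500 mg, 5 h replaces 1.5 h.
- Overlap: 1, 2, 3, 4, 6, 9, 12 and 24 h = 8 of 11. Not covered: 0.5, 1.5 and 2.5 h in the lower cohorts; 0.5, 2.5 and 5 h in the higher ones.

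**4. Precision and number of estimates under the fix**

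With placebo pooled over cohorts, each dose compares 6 active with 16 placebo subjects up to 72 h. At 96 and 120 h there are 4 × 2 = 8 placebo subjects. No SD is given, so half-widths of a 90% CI are in units of the between-subject SD of the change from baseline (σ), assuming a common variance and complete data:

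- Up to 72 h: t(20 df) × √(1/6 + 1/16) = 1.725 × 0.479 = 0.83σ.
- At 96 and 120 h: t(12 df) × √(1/6 + 1/8) = 1.782 × 0.540 = 0.96σ.

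σ is larger for single ECGs than for averaged triplicates. The protocol does not allow the size of that difference to be calculated.

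Number of intervals per parameter: 4 × 10 + 4 × 12 = 88. For HR, PR, QRS, QT, QTcF and QTcB: 6 × 88 = 528. If there were no effect at all, about 0.10 × 528 = 53 of these 90% intervals would be expected to exclude zero.

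**The case against.** **The cardiac objective does not go unanswered without MAD.** A reader might infer that it does. The documents do not support that. Of the 3.1.3 parameters, HR, PR, QRS, QT, QTcF and QTcB are recorded, centrally read and described with their changes from baseline in every case (8.1.1.3, 11.1.2.2). RR follows from HR. The 12-lead ECG is also a primary safety endpoint (3.1.1), and centrally read ECGs reach the Safety Review Committee after each cohort (3.3.3.2). If placebo is tabulated as its own group, a reader could even derive a rough difference from the means, SDs and counts listed in 11.1.1. This stands and limits the finding to the formal PD analyses.

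**Placebo correction is not promised everywhere.** It is in the Synopsis and, in narrower form, in Section 7. The objective in 2.3 and the endpoint list in 3.1.3 do not mention it. This also stands.

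**Results-dependent reporting is an inference.** A reader might conclude that an ECG finding would stop development and so suppress its own analysis, or that this is the case in which a signal matters most. The protocol gives no criteria for the MAD decision; it links the centrally read ECGs to dose escalation within this trial. Where a signal matters most is opinion: a small QTc effect may matter more when dosing continues. The archived recordings also leave later analysis possible.

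**Staged Holter analysis is a legitimate choice** for an exploratory objective. That is so, but the Synopsis should then say the same. It makes only one of the analyses optional.

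**Conclusion.** The contradiction is real and lies between the Synopsis, with the unconditional wording of 2.3 and 3.1.3, and Sections 7 and 11.1.3. If no MAD study follows, the placebo-corrected estimates, the QTc threshold counts and the concentration-QTcF model are not provided for, and the cardiac result is limited to descriptive safety tables. Section 11.1.3 would not deliver the Synopsis sentence even with MAD, since it lists no placebo-corrected analysis by time point.

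Severity is minor to moderate. The objective is exploratory, the primary safety conclusions are unaffected, and most of the listed parameters are summarised in any case. The conclusion rests on reading both branches of the Section 7 timing sentence as requiring a MAD study; no other passage suggests otherwise.

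**What to change.** - In 3.1.3, 7 and 11.1.3, state that in all cases the placebo-corrected change from baseline with 90% CI is reported by dose and nominal time from the centrally read 12-lead ECGs. Use pooled placebo and the mean of the D1 triplicate as baseline. Cover HR, PR, QRS, QT, QTcF and QTcB, with RR derived from HR.
- Amend the sentence in 11.1.3 that makes Holter the sole source for the PD analysis.
- Keep the Holter triplicates and the concentration-QTcF model as the add-on that depends on the MAD decision, and make the Synopsis agree with Sections 7 and 11.1.3 on which analyses are conditional.

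The cost is extra tables from data already in the clinical database, with no new procedure or reading. The intervals will be wider than with Holter triplicates, three of the eleven Holter times per cohort are missed, and there will be many unadjusted intervals, so the result should be labelled exploratory.

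Making the objective, endpoints and Synopsis conditional in the same words as Section 7 would also remove the contradiction, but would leave no placebo-corrected result without MAD.

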4. STUDY POPULATION

4.1. Subject inclusion criteria

For eligibility into the trial, subjects must meet all the following inclusion criteria:

- 1- Healthy Caucasian male subject aged 18 to 50 years inclusive.
- 2- Non-smoker subject or light smoker of not more than 5 cigarettes a day. No smoking (or use of smoking substitute e.g. nicotine patch) is permitted from screening throughout the study;
- 3- Body Mass Index (BMI) between 18 and 30.1 kg/m² inclusive at screening;
- 4- Considered as healthy after a comprehensive clinical assessment (detailed medical history and complete physical and neurological examination);
- 5- Normal Blood Pressure (BP) and Heart Rate (HR) at the screening visit after 10 minutes in supine position:
 - o 95 mmHg ≤ Systolic Blood Pressure (SBP) ≤ 140 mmHg,
 - o 50 mmHg ≤ Diastolic Blood Pressure (DBP) ≤ 90 mmHg,
 - 45 bpm \leq HR \leq 90 bpm,
 - Or considered NCS by investigators;
- 6- Normal ECG recording on a 12-lead ECG at the screening visit:
 - o 120 ms ≤ PR ≤ 210 ms,
 - o QRS < 120 ms,
 - QTcf \leq 430 ms for male,
 - No sign of any relevant trouble of sinusal automatism
 - o Or considered as non-clinically significant by investigators,
- 7- Laboratory parameters within the normal range of the laboratory (hematological, hormonology, blood chemistry tests, urinalysis). Individual values out of the normal range can be accepted if judged non-clinically significant by the Investigator; for example, isolated elevated bilirubin is acceptable if judged by the physician without clinical relevance (i.e. Gilbert's syndrome)
- 8- ALAT, ASAT and Creatinine values strictly within the normal range
- 9- A negative result for diagnostic test of SARS-CoV-2 at D-1
- 10- Normal dietary habits;
- 11- Provision of written informed consent to participate as shown by a signature on the volunteer consent form, after reading the information and consent form, and after having the opportunity to discuss the trial with the investigator or his delegate;
- 12- Able to communicate well with the Investigator and research staff and to comply with the requirements of the entire study;
- 13- Covered by Health Insurance System and / or in compliance with the recommendations of National Law in force relating to biomedical research;

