Categorical analysis consisting in counts and percentages of abnormal values per dose level will be performed for HR, QTc, PR and QRS according to regulatory thresholds for raw data and changes from baseline.

Treatment emergent morphological findings will be summarized as counts and percentage of subjects presenting at least one finding by dose level.

Concentration-response relationship will be investigated between change from baseline in QTcF and DNDI-6148 concentrations. First, graphics of change from baseline in QTcF and concentrations of DNDI-6148 will be generated in order to visualize the overall pattern of each relationship. Modelling of each of these graphics will then be performed by means of linear or nonlinear mixed model.

For each compound, a model will be selected according to the overall precision of the model towards observed data and diagnostic plots. Using these models, predictions of changes from baseline at concentrations of interest (e.g. Cmax) will be obtained from the concentration-response models with their 90%CI.

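### The absolute QTc categories (above 450, 480 and 500 ms) are counted per dose level without reference to the pre-dose baseline, so a QTcB already above 450 ms before dosing can appear as an exceedance on the dose

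*Protocol*

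**What the plan says.** Protocol Section 7 (Assessment of pharmacodynamic evaluation) plans a "Categorical analysis for QT, QTcF, QTcB, ΔQTcF and ΔQTcB according to the thresholds defined below". It introduces the absolute cut-points with "The pre-defined thresholds for the categorical analysis for maximum actual values will be", and the lowest is "QTc interval > 450 ms", followed by 480 and 500 ms. A second list applies to maximum changes from baseline and begins with "ΔQTc interval > 30 ms", followed by 60 ms. The baseline is defined: "On Day 1, three pre-dose triplicates will be extracted and averaged to establish the baseline value".

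Section 11.1.3 (Pharmacodynamic) sets the reporting: "Categorical analysis consisting in counts and percentages of abnormal values per dose level will be performed for HR, QTc, PR and QRS", on raw data and on changes from baseline. The next sentence treats morphology differently: "Treatment emergent morphological findings will be summarized as counts and percentage of subjects".

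Section 4.1 sets the entry limits at screening. Criterion 6 caps QTcF at 430 ms and gives QTcB no limit. It ends with the alternative "Or considered as non-clinically significant by investigators", which has no upper bound. Criterion 5 accepts a supine heart rate of 45 to 90 bpm, with a similar override.

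**The concern.** The treatment-emergent idea is applied to one ECG category and not to the one beside it. An absolute category based on the maximum actual value counts a subject whose QTc was above the cut-point before he took anything, and lists him under his assigned dose. The wording also does not limit the maximum to post-dose extracts, and T0 is among the listed extraction times. Even if the maximum is taken post-dose only, a stable pre-existing elevation is still counted.

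Entry would make this harmless only if it kept everyone below 450 ms in both corrections. It does not do so for QTcB, which rises relative to QTcF as heart rate rises. With six active subjects per dose level, a single pre-existing exceedance visibly changes the dose-level percentage and could be read as a drug finding.

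**Working it through.** The protocol states no figure to reproduce here. The check asks whether a subject inside the numeric entry limits can have QTc above 450 ms before dosing.

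**Inputs.** QTcF at most 430 ms (Section 4.1, criterion 6); heart rate at most 90 bpm (criterion 5); lowest threshold 450 ms (Section 7); six active and two placebo subjects per cohort, eight cohorts (Section 3.3.3.1).

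**Formula.** With RR = 60/HR in seconds, QTcF = QT/RR^(1/3) and QTcB = QT/RR^(1/2). Hence QTcB = QTcF × (HR/60)^(1/6).

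**Results**

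| HR (bpm) | QTcB at QTcF 430 ms | QTcF at which QTcB = 450 ms |
|---|---|---|
| 60 | 430.0 | 450.0 |
| 70 | 441.2 | 438.6 |
| 75 | 446.3 | 433.6 |
| 80 | 451.1 | 428.9 |
| 85 | 455.7 | 424.6 |
| 90 | 460.1 | 420.6 |

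- Heart rate at which QTcB reaches 450 ms with QTcF 430 ms: 60 × (450/430)^6 = 78.8 bpm.
- At 90 bpm, any QTcF above 450/1.5^(1/6) = 420.6 ms gives QTcB above 450 ms.
- The highest QTcB inside the numeric limits is 430 × 1.5^(1/6) = 460.1 ms. Within those limits only the 450 ms category can be exceeded at entry, not 480 or 500 ms.
- For QTcF, exceeding 450 ms at entry means being more than 450 − 430 = 20 ms over the limit. That is possible only through the override.

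**Weight of one subject.** 1/6 = 16.7% of an active dose group. The pooled placebo group, if all eight cohorts are completed, is 8 × 2 = 16 subjects, where one is 1/16 = 6.25%.

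**Which outputs are touched.** The ΔQTc categories subtract the baseline, as do the placebo-corrected changes (ΔΔ) in the synopsis and the ΔQTcF concentration-response model in Sections 7 and 11.1.3. Only the raw-value category counts lack a baseline reference.

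**The case against.** **The SAP may settle it.** How a category is attributed is often left to the SAP and table shells, and a plan that is not shown may add a treatment-emergent rule. That is fair, but the protocol is not merely silent: it fixes the basis as the maximum actual value in both corrections, and limits only the neighbouring morphological findings to treatment-emergent ones.

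**Baseline is handled elsewhere.** The ΔQTc categories, ΔΔ with 90% CI, individual listings and concentration model all bring baseline in, so a reader with all the outputs could recognise a pre-existing elevation. This stands, and it keeps the point small. It does not correct the raw-value table itself.

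**The situation may be rare.** Within the numeric limits it needs QTcF of about 421 to 430 ms together with a heart rate of about 79 to 90 bpm, and Section 7 takes the Holter extracts during supervised supine rest. The protocol gives no distribution of QTc or heart rate, so the frequency is unknown. The 17% is one subject's contribution, not an estimate of bias.

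A reader might infer more than the documents support:

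- *That the entry criteria readily admit QTcF above 450 ms.* They do so only by override, under a criterion requiring a normal ECG and alongside exclusion criterion 3 on clinically significant abnormalities.
- *That the cardiac conclusion or dose escalation rests on these counts.* The comparative reading rests on baseline-referenced analyses, and Section 3.3.3.2 bases escalation on the separate safety ECGs and their central reading.
- *That the 4-hour ECG is inflated by lunch.* Extraction precedes the blood draw (Section 7) and meals follow it (Section 8.2.3), so that extract is taken before the meal.
- *That QTcB should be removed.* It is a named exploratory endpoint in Section 3.1.3, and dropping it would be a preference.

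**Conclusion.** The point holds as a minor one. As fixed in the protocol, the absolute QTc categories can place a pre-dose exceedance under a dose. Within the numeric entry limits this concerns QTcB and the 450 ms category only, from about 79 bpm at QTcF 430 ms. For QTcF it requires the investigator's override. Each affected subject adds 1 of 6 to an active group's count in a table that is exploratory, descriptive and produced only if the Holter data are analysed. Since Section 7 foresees pooling with a multiple-dose study, the definition may be carried forward.

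This rests on three assumptions. Counting is by subject, as the synopsis and the use of a maximum suggest, although Section 11.1.3 speaks of abnormal values. Pre-dose values on Day 1 are similar to those at screening, where the limits apply. No unseen document already adds a baseline condition.

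**What to change.** In Sections 7 and 11.1.3:

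1. Restrict the maximum to post-dose extracts and count subjects.
2. Tabulate, by dose level and for pooled placebo, each subject's highest post-dose category against the category of his averaged pre-dose Holter baseline. Report as treatment-emergent only those whose post-dose category is higher than at baseline.
3. Show baseline exceedances separately, with the baseline and the highest post-dose value. Simply excluding these subjects would hide real worsening. For example, a rise from 452 to 475 ms stays below 480 ms and is a change of 23 ms, below the 30 ms category, so it would appear nowhere.
4. Keep QTcB as a named endpoint, but read the categories primarily on QTcF, the correction used for entry and for the concentration-response model.

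The cost is wording and programming: the baseline is already to be extracted, and no visit, subject or measurement is added. Two limits remain. The baseline is an average of three triplicates while the post-dose value is the largest of 11 extracts, so some new exceedances will arise by chance and should be read against placebo. The shift table also does not remove a QTcB exceedance produced after dosing by a faster heart rate, which is the reason for reading QTcF first.
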